### ***13.3 Informed Consent Process***

#### ***13.3.1 Consent/Accent and Other Informational Documents Provided to Participants***

CONFIDENTIAL

This material is the property of the NYU Langone Health. Do not disclose or use except as authorized in writing by the study sponsor

Consent forms describing in detail the study intervention, study procedures, and risks are given to the participant and written documentation of informed consent is required prior to participating in any study activities.

### **13.3.2 Consent Procedures and Documentation**

All informed consent will be completed following the HIPAA compliant, remote e-Consenting method approved by NYU Langone Health. A potential caregiver participant will first be screened remotely through a telephone call with PIs (or be pre-screened by a research assistant during a recruitment call and then formally screened by the PIs via phone) to confirm eligibility. If the caregiver is eligible and wishes to participate, PIs will then schedule a follow-up Zoom call (via HIPAA compliant Zoom) with the caregiver to complete the e-Consenting process together in REDCap. A copy of the consent form will be emailed or mailed to the potential caregiver subject in advance to review before the consenting Zoom call. During the HIPAA compliant Zoom call, PIs will share the screen and go over the IRB-approved REDCap e-consent and HIPAA authorization form, page by page, with the caregiver. The e-consent process informs the potential caregiver participant about the study, describes potential risks and benefits, indicates that the participation is voluntary and that he/she has the right to stop at any time. PIs will also provide the potential caregiver participant contact information in case of medical emergency due to study participation and questions about subject rights, as well as explain who have access to study data and protected health information, how confidentiality is maintained, how the participant may receive the outcome of the study and incentives for study participation.

PIs will ensure that the eligible caregiver has the opportunity to consider whether to participate and ask questions before electronically signing the consent and HIPAA authorization form in REDCap during the Zoom call, as well as at anytime during their involvement in the research study. If the caregiver decides to give consent, PIs will give the caregiver remote control over the mouse of the PI's device to initial and sign the REDCap e-consent and HIPAA authorization form in REDCap. After signing electronically, the caregiver will receive an electronic copy of the signed consent and HIPAA authorization form immediately in an automatically generated email from REDCap. If caregivers have difficulty signing through remote control over the PI's mouse, then a link to the REDCap e-consent form will be emailed to the caregiver to sign and initial in REDCap. Caregivers enrolled in the feasibility study phase will have the option to include additional secondary caregivers, who will undergo the same e-Consenting process. Electronic informed consent and HIPAA authorization documents with subject information will be collected, stored, and maintained on the password-protected REDCap system with 2 factor-authentication. Only authorized study team members will have access to the consent and HIPAA authorization forms stored in REDCap.

### **13.3.3 Waiver of Authorization/Consent**

The following is applicable to Aim 2 feasibility trial only:

The study team will obtain a waiver of authorization/consent to view the patient's discharge status in EPIC to determine whether and when to contact the potential caregiver participants referred by the inpatient geriatrics consult teams (see **5.4.4 Clinician Referral**). According to feedback from the inpatient geriatric consult team, caregivers are too overwhelmed to consider study participation when their loved one is still in the hospital. The referral clinician suggests that the study team reaches out to caregivers only after their loved one is discharged. Because the referral clinician cannot predict the discharge date and location in advance and suggests that after they have made the referral, the study team monitors the patient's discharge status in EPIC to determine whether and when to follow up with their caregiver about study participation.

### **13.4 Posting of Clinical Trial Consent Form**

Not applicable.

CONFIDENTIAL

This material is the property of the NYU Langone Health. Do not disclose or use except as authorized in writing by the study sponsor

## **13.5 Participant and Data Confidentiality**

Information about study subjects will be kept confidential and managed according to the requirements of the Health Insurance Portability and Accountability Act of 1996 (HIPAA). Those regulations require a signed subject authorization informing the subject of the following:

- What protected health information (PHI) will be collected from subjects in this study
- Who will have access to that information and why
- Who will use or disclose that information
- The rights of a research subject to revoke their authorization for use of their PHI.

In the event that a subject revokes authorization to collect or use PHI, the investigator, by regulation, retains the ability to use all information collected prior to the revocation of subject authorization. For subjects that have revoked authorization to collect or use PHI, attempts should be made to obtain permission to collect at least vital status (i.e. that the subject is alive) at the end of their scheduled study period.

Participant confidentiality is strictly held in trust by the participating investigators, their staff, and the sponsor(s) and their agents. This confidentiality is extended to cover testing of biological samples and genetic tests in addition to the clinical information relating to participants. Therefore, the study protocol, documentation, data, and all other information generated will be held in strict confidence. No information concerning the study or the data will be released to any unauthorized third party without prior written approval of the sponsor.

The study monitor, other authorized representatives of the sponsor, or representatives of the IRB may inspect all documents and records required to be maintained by the investigator, including but not limited to, medical records (office, clinic, or hospital) and pharmacy records for the participants in this study. The clinical study site will permit access to such records.

The study participant's contact information will be securely stored in REDCap for internal use during the study. At the end of the study, all records will continue to be kept in a secure location for as long a period as dictated by local IRB and Institutional regulations.

Study participant research data, which is for purposes of statistical analysis and scientific reporting, will be deidentified and stored in a password-protected NYU Box folder. This will not include the participant's contact or identifying information. Rather, individual participants and their research data will be identified by a unique study identification number. The study data entry and study management systems used by the study team will be secured and password protected.

### **13.5.1 Research Use of Stored Human Samples, Specimens, or Data**

Data collected from this study will be deidentified and shared following NIH's data sharing policy as appropriate.

## **13.6 Future Use of Stored Specimens**

NA.

# **14 Data Handling and Record Keeping**

## **14.1 Data Collection and Management Responsibilities**

A research assistant trained by the PI will conduct phone recruitment and log phone screening/recruitment results in REDCap (e.g., interested/declined/did not answer). The PIs will collect the rest of the study data and will be responsible for managing and validating of all study data.

CONFIDENTIAL

This material is the property of the NYU Langone Health. Do not disclose or use except as authorized in writing by the study sponsor

### 14.1.1 Data Collection in REDCap Online Survey Questionnaires

PIs will complete measures specified in Table 3 and Table 4 in REDCap online survey questionnaires based on caregiver report.

Table 3. Aim 1 Measures (In the Form of Online REDCap Survey Questionnaires)

Variable	Measure	Administration Time (mins) a
Caregiver and care recipient demographics information	Demographic questionnaires developed by the study team.	5
DSD exposure	Did you provide care to or visit your loved one when he/she had a delirium episode within the past 12 months? (Yes/No)	<1
Health literacy	BRIEF Health Literacy Screening (4 items)	2
Comfort with technology	Functional Assessment of Currently Employed Technology Scale (10 items)	3

Table 4. Aim 2 Measures (in the Form of Online REDCap Questionnaires)

Variable	Measure	Administration Time (mins)	Timeline a		
			Baseline/ enrollment (Week 0)	Immediately post training (Week 2)	Posttest (Week 6)
Caregiver and care recipient demographics information	Demographic questionnaires developed by the study team	5	Yes	-	-
Health literacy	BRIEF Health Literacy Screening (4 items)	2	Yes	-	-
Comfort with technology	Functional Assessment of Currently Employed Technology Scale (10 items)	3	Yes	-	-
Dementia Severity	Quick Dementia Rating System (10 items)	4	Yes	-	-
Behavioral and psychological symptoms of dementia	Neuropsychiatric Inventory Questionnaire (12 items)	5	Yes	-	-
Caregiver strain	Modified Caregiver Strain Index (13 items)	5	Yes	-	Yes
Caregiver Depression	Center for Epidemiological Studies Depression Scale (20 items)	4	Yes	-	Yes
Caregiver Burden	Short Form Zarit Burden Interview (12 items)	3	Yes	-	Yes
General caregiving self-efficacy	Revised Scale for Caregiving Self-Efficacy (15 items)	3	Yes	-	Yes
DSD Caregiving Mastery	A DSD Competence Scale modified from Pearline's Competence Scale with	5	Yes	Yes	Yes

CONFIDENTIAL

This material is the property of the NYU Langone Health. Do not disclose or use except as authorized in writing by the study sponsor

	additional items developed by the Aliviado team to assess confidence and completion of DSD prevention, detection, and management tasks (14 items)				
Caregiver Delirium Knowledge	Caregiver Delirium Knowledge Questionnaire (19 items)	5	Yes	Yes	Yes
Program satisfaction	13 Likert-type questions to assessment program satisfaction and willingness to recommend the program plus one optional open-ended question to provide additional feedback (14 items total)	3-5	-	-	Yes
Usability	A modified IBM Computer Usability Satisfaction Questionnaire developed by the Aliviado team (24 Likert-type questions + 3 optional open-ended questions to provide additional feedback)	5-10	-	-	Yes

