## **2.3 Potential Risks & Benefits**

### **2.3.1 Known Potential Risks**

This is a minimal risk study. The intervention itself is inherently not risky as it is a family-centered, psychoeducational training program on implementation of evidence-based best practices through an mHealth app to improve family caregivers' mastery in performing DSD detection, prevention, and symptom management tasks. The greatest potential risks to family caregiver subjects are (1) a breach of confidentiality and (2) psychological distress.

Though possible, we anticipate that a breach of confidentiality is unlikely to happen because personal identifiers will only be collected and stored in the password-protected REDCap electronic consent and HIPAA authorization form, in which only authorized study team members will have access to, whereas all the other study data will be deidentified and stored in a password-protected NYU Box folder, in which access will only be granted to appropriate study team members. NYU Box is the NYU WSQ Campus approved storage of [high-risk data](#).

When learning something new such as a new mHealth app, some caregivers can become frustrated or experience psychological distress. However, we believe psychological distress is unlikely to happen, because we will have tested our mHealth app to ensure user-friendliness. We will also proactively offer additional technical support/training sessions on how to use the study app via Aliviado Support Center ([contact]) to caregivers who report a lower level of comfort with technology at enrollment (caregivers are free to decline this offer/additional support). If caregiver subjects experience psychological distress or become frustrated with the technology, they can contact Aliviado Support Center ([contact]) for assistance. If participants do not feel comfortable answering depressive symptom questions or any questions in any of the study questionnaires, they have the option to select "prefer not to answer" as their response. Subjects may also experience psychological distress when answering questions about their depressive symptoms and will also have the option to select "prefer not to answer".

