**Week 6 Final Visit (n=30 primary caregivers + up to 30 secondary caregivers)**

- Collect data on caregiver participants’ delirium knowledge, DSD caregiving mastery, caregiver strain, depressive symptoms, burden, program satisfaction, and app usability in an online REDCap survey questionnaire.

Also see Attachment C for schedule of events.

\*We will stick with CES-D to collect data on depressive symptoms. We were considering replacing it with PHQ-9 because PHQ-9 is a shorter questionnaire. We decided to still use CES-D because it does not ask about suicidal ideation. All de-identified baseline caregiver depressive symptom raw scores will only be analyzed as a group and presented as mean/sd/range (or median/interquartile range/range if not normally distributed).

If a high level of symptoms are found from CES-D, such as depressive symptoms, we will offer to refer subjects to support services that may help with these, such as the NYU Alzheimer’s Caregiving Program. This information will remain confidential and will not be shared with others.

CONFIDENTIAL

This material is the property of the NYU Langone Health. Do not disclose or use except as authorized in writing by the study sponsor

If a high level of caregiving strain is found, we will offer to refer subjects to support services that may help, such as the NYU Alzheimer's Caregiving Program, however this information will remain confidential and will not be shared with others. If the depressive symptom score has increased for 15 or more points from the baseline/enrollment visit for a subject, our medical monitor, [name], (a board-certified nurse practitioner) will call the subjects to better understand their change in depressive symptoms; determine whether it is related to their study participation; and will refer them to mental health or emergency services as needed.

*Rationale for change score:* We will calculate the mean and range of the change score from baseline to posttest as a group (=all caregivers' scores lumped together).

If the upper limit of the range of the group change score is below 15, then it means that no one in the group has a substantial increase in their depression score and we will not reach out to any participants about their depressive symptoms.

If the upper limit of the range of the group change score is 15 or above (out of the 60-point CES-D scale), we will look up the participants who have a change score  $\geq 15$  and notify the medical monitor.

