## **7.3 Study Schedule**

All visits will be completed through phone or Via HIPAA-Compliant Zoom.

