#### 7.3.4 Final Study Visit

Aim 1 codesign workshop: See 7.3.3 above for information about the fifth co-design session. An optional 30-minute, 1:1 user testing session will be scheduled with 5-6 volunteers from Aim 1 participants and waitlist to test the beta version of the new caregiver mHealth app developed based on co-design workshop feedback in-between the 2 study phases. The fifth co-design session and the 1:1 session will both be video recorded along with live chat via HIPAA Compliant Zoom.

Aim 2 feasibility trial: The final 1:1 study visit will be scheduled in Week 6 (+/-5 days) to collect data on the following using online REDCap survey questionnaires:

- ✓ Caregiver strain
- ✓ Depression
- ✓ Caregiver burden
- ✓ Caregiver delirium knowledge
- ✓ DSD caregiver mastery
- ✓ Program satisfaction
- ✓ App usability

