## **11 Source Documents and Access to Source Data/Documents**

All data collected for this study will be maintained in an electronic format. All e-Consent and HIPAA documents will be collected and stored on the password-protected REDCap system with 2 factor-authentication. All surveys will be collected through online NYU REDCap survey questionnaires, cleaned, deidentified, and uploaded to a secure folder in PI [name]'s password-protected NYU Box research space with

CONFIDENTIAL

This material is the property of the NYU Langone Health. Do not disclose or use except as authorized in writing by the study sponsor

2 factor-authentication. Where there are unanticipated problems, adverse events or serious adverse events, the corresponding report forms will be filled out and maintained in REDCap. Protocol deviation forms will be filled out and maintained in a secure folder within PI [name]'s NYU Box research space for reporting purposes. PI [name] will be responsible for creating and maintaining an electronic study binder in REDCap. During weekly meetings, PI [name] and PI [name] will review all forms completed in the previous week to ensure accuracy, as well as edit/update the forms as needed. All corrections made will be recorded in a Data Management Log in a secure folder within PI [name]'s NYU Box research space and be updated and maintained by both PIs.

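### As written, caregivers give their Week 6 satisfaction and usability ratings live to the PIs who lead the program, which risks upward courtesy bias of unknown and possibly small size

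*Combined protocol and SAP*

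**What the plan says.** Section 14.1.1 assigns completion of the questionnaires to the investigators: "PIs will complete measures specified in Table 3 and Table 4 in REDCap online survey questionnaires based on caregiver report". Table 4 in that section lists two instruments given only at Week 6. One is a program-satisfaction questionnaire with 13 Likert-type items, which cover willingness to recommend the program. The other is a modified usability questionnaire ("24 Likert-type questions + 3 optional open-ended questions to provide additional feedback").

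Section 14.1 gives phone recruitment and its log to a research assistant, then adds: "The PIs will collect the rest of the study data". Section 7.3 says: "All visits will be completed through phone or Via HIPAA-Compliant Zoom". Section 7.3.4 makes the last contact individual ("The final 1:1 study visit will be scheduled in Week 6 (+/-5 days") and lists satisfaction and usability among the data collected there.

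Section 4.2.1 makes both instruments part of the primary endpoints. Acceptability criterion 1 needs more than 80% of primary caregivers to report high satisfaction and willingness to recommend. Usability is measured at Week 6 with no pass mark. Section 10.4.2 plans descriptive estimates with 95% confidence intervals.

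Other sections describe the mode less fully. Section 7.1.1 (Week 6 Final Visit) has "program satisfaction, and app usability in an online REDCap survey questionnaire", and Section 11 has "All surveys will be collected through online NYU REDCap survey questionnaires". Neither says who fills in the form. Section 2.3.1 tells participants who are uncomfortable with "any questions in any of the study questionnaires, they have the option to select" a decline-to-answer response. Section 5.5 says care-recipient information comes through survey links sent to the caregiver.

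**The concern.** Section 16.1 names the PIs as co-leads of the project. Under Section 6.1.1, questions about assessments and care-plan tasks are forwarded to the PI, who also offers a goal-setting call to caregivers with low self-efficacy. A caregiver asked by one of these people, live, how satisfied they are and how usable the app is may soften criticism. Any such effect would probably push ratings upward.

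Two results are exposed: criterion 1, which has a fixed threshold, and the usability estimate. A confidence interval describes sampling error, so it would not show a shift in how people answer. Section 2.2 says the findings will guide refinement before an efficacy trial, so candid criticism is much of what the pilot is meant to collect.

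**Working it through.** **1. Who takes the ratings.** Sections 14.1 and 14.1.1 name the PIs as collecting the data and completing the forms. Sections 7.3 and 7.3.4 make the occasion live and one-to-one. Together they have the caregiver state the ratings to a PI. No section gives a safeguard for these two forms. The decline-to-answer option in Section 2.3.1 permits non-response but does not make an answer more candid.

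**2. Is the mode consistent?**

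| Table 4 rows | Section 14.1.1 | Elsewhere |
|---|---|---|
| Satisfaction, usability (Week 6) | PI completes | Sections 7.1.1, 7.3.4 and 11 name the platform only, so there is no contradiction |
| Care-recipient rows (baseline) | PI completes | Section 5.5: links sent to the caregiver, which conflicts |
| Any questionnaire | PI completes | Section 2.3.1 has participants select the response, which hints at self-completion |

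**3. Which endpoints are exposed.** Criterion 1 and usability are. Criteria 2 (videos completed) and 3 (at least two weekly screenings) rest on completion records, which Sections 6.1.2 and 14.1.2 describe as tracked automatically.

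**4. How sensitive criterion 1 is to a shift.** The plan gives no bias figure to reproduce. Its sample sizes do reproduce: Section 10.5 has 26 evaluable and 12% dropout, and 26/0.88 = 29.5, rounded up to 30. The denominator for criterion 1 is not fixed, so both are used. There is also no stated cut-off for high satisfaction, so each caregiver is treated as yes or no.

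Count needed to exceed 80%:
- n = 26: 20/26 = 76.9% fails and 21/26 = 80.8% passes.
- n = 30: 24/30 = 80.0% fails and 25/30 = 83.3% passes.

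Chance of passing: P(X ≥ k) = Σ C(n,x) p^x (1−p)^(n−x), summed over x = k to n. Every true and reported rate below is an assumption.

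| True rate → reported rate | n = 26, k = 21 | n = 30, k = 25 |
|---|---|---|
| 50% → 60% | 0.1% → 2% | under 0.1% → 0.6% |
| 60% → 70% | 2% → 16% | 0.6% → 8% |
| 70% → 75% | 16% → 34% | 8% → 20% |
| 70% → 80% | 16% → 58% | 8% → 43% |
| 90% → 95% | 96% → 99.8% | 93% → 99.7% |

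(Unrounded, n = 26 at 50% is .0012.) The shift matters near the threshold and little far from it.

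**5. What skipped forms would do under self-completion.** Take n = 26, an assumed 2 or 4 missing forms, and responders positive at the assumed true rate.

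| Missing | Counted as not met: needed | Chance at 85% | Chance at 90% | Excluded: needed | Chance at 85% |
|---|---|---|---|---|---|
| 0 | 21/26 (81%) | 82% | 96% | 21/26 (81%) | 82% |
| 2 | 21/24 (88%) | 50% | 79% | 20/24 (83%) | 71% |
| 4 | 21/22 (95%) | 14% | 34% | 18/22 (82%) | 77% |

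**The case against.** The strongest reply has three parts.

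First, Section 14.1.1 may be loose drafting. Section 2.3.1 speaks of participants selecting answers, and the Week 6 text in Section 7.1.1 does not mention a PI entering them. That is possible, but then Section 14.1.1 is wrong and needs correcting.

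Second, the bias is conjectural. The program is mainly self-paced videos and app tasks, and the PI's individual call is offered only to some caregivers (Section 6.1.1). Criterion 1 is one of three acceptability indicators, usability has no pass mark, and no go/no-go rule is attached. All of this stands, and it keeps the point modest.

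Third, assisted completion is defensible where some caregivers have low health literacy or low comfort with technology, and self-completion can cost data. Step 5 shows that if skipped forms count as failures, a few of them can move criterion 1 as much as the assumed bias does. This stands as a condition on the fix: missing forms must be few and reported openly. It does not support leaving the ratings with the PIs.

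Some stronger readings are tempting but not supported:

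- *The mode is contradictory for the satisfaction and usability rows.* It is not. The explicit conflict concerns the baseline care-recipient rows.
- *The word anonymous in Sections 6.1 and 7.1.1 shows self-completion.* Both passages explain it as collecting no care-recipient identifiers. Only Section 5.5 speaks of links sent to the caregiver.
- *The single-arm design is why the bias cannot be removed.* An untreated control group could not rate this program, so a control arm would not remove the bias either.

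**Conclusion.** The point holds as a matter to consider. Read as written, Sections 14.1 and 14.1.1 with 7.3 and 7.3.4 have caregivers give two subjective primary-endpoint ratings live to the program's leaders, with no safeguard. The likely direction of any bias is upward. Its size is unknown, may be small, and cannot be derived from the documents.

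A reader might infer that the acceptability or usability results will be inflated. The documents support a risk and no more. The probabilities in step 4 rest wholly on assumed true rates and shifts, with satisfaction treated as yes or no. They show only that a 5- to 10-point shift could change the verdict on criterion 1 when the true rate lies near 80%. Criteria 2 and 3 and the sample-size calculation are untouched.

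The mismatch between Section 14.1.1 and Sections 5.5 and 2.3.1 is a separate drafting matter. Its explicit part concerns descriptive baseline data.

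**What to change.** Amend Section 14.1.1 so that caregivers complete the Week 6 satisfaction and usability questionnaires themselves, through an individual REDCap link and with no PI on the call. Send reminders within the ±5-day window of Section 7.3.4. Offer technical help on request from the Support Center and log it. Report the number of missing forms, and show criterion 1 both among responders and with missing forms counted as not met. State who completes each Table 4 row, so that Section 14.1.1 agrees with Sections 5.5 and 2.3.1.

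The cost is a protocol amendment with IRB approval before use (Sections 13.2 and 14.3), the set-up of links tied to the study ID, and possibly a few skipped forms. Section 5.5 describes anonymous links, so the individual ones are a related but not identical use. The $50 Week 6 payment (Section 15.3) should help completion.

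The bias would be reduced, not removed. Answers stay linked to the participant, the PIs review forms weekly (Section 9), and Support Center staff belong to the same program.
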